## 11.9 REPORTS TO THE DSMB, STUDY INVESTIGATORS, IRBS, AND OTHER AUTHORITIES

### 11.9.1 SERIOUS ADVERSE EVENTS

The site investigator, the Principal Investigator, and the SDMC SAE Regulatory Specialist will collaborate to prepare a MedWatch 3500A report for any SAE that is fatal. The Principal Investigator will submit the report to (a) the Chair of the DSMB

Subcommittee appointed to monitor this study and to (b) the NHLBI Project Officer within 15 calendar days of initial notification to the SDMC SAE Regulatory Specialist.

If a safety signal is detected, a Dear Investigator Letter will be sent via the SDMC to all site study investigators. Each study investigator will submit the SAE report to the local IRB in accordance with the institution's regulations.

**TABLE 11.3 Summary of Procedures and Timing for Alerting the DSMB and NHLBI Project Officer of Possible Serious Safety Issues**

Situation or Event	Summary of Procedure (See text for details.)	Critical Value for DSMB "Alert"	Frequency
SAEs reported with a SAE Criterion of Death	DSMB will be notified of all SAEs that are reported with a SAE criterion of Death within 15 days of the SDMC SAE Regulatory Specialist becoming aware of the event.	Death	15 calendar days from SDMC notification
SAEs (all)	SDMC performs quarterly analyses of MedDRA-coded SAEs, tabulates patients with SAEs classified by highest level MedDRA term. Report only when $p < \text{critical value}$ and active treatment group has higher AE rate.	$p < 0.01$ $p$ not adjusted for multiplicity	Quarterly if meets critical alert value
SAEs (all)	SDMC performs semi-annual analyses of MedDRA-coded SAEs, tabulates patients with SAEs classified by highest level MedDRA term.	Report all cases	Semi-annual
AEs (all)	SDMC performs semi-annual analyses of MedDRA-coded AEs, tabulates patients with AEs classified by highest level MedDRA term. Report every six months. Alert only when FET $p < \text{critical value}$ and active treatment group has higher AE rate.	$p < 0.01$ $p$ not adjusted for multiplicity	Semi-annual if meets critical alert value
Transfusion Reactions	The SDMC will report the following events semi-annually to the DSMB, regardless of incidence rates: 
 
• Development of clinically significant alloantibodies
 
• Development of autoantibodies associated with hemolysis that result in inability to transfuse safely.
 
• Development of clinically significant hemolytic transfusion reactions.
 
	Report all cases	Semi-annual
Clinical Laboratory Results	
 
• SDMC performs semi-annual analyses of clinical laboratory (hemoglobin and ferritin) change-from-baseline data for each clinical laboratory evaluation obtained in this study.
 
	Report all cases	Semi-annual

## 12 DATA COLLECTION AND DATA MONITORING

### 12.1 CRF AND SOURCE DOCUMENTATION

The site study coordinator will complete a case report form (CRF) for each subject. A CRF manual will be provided to each site to assist in correct CRF completion. A paper copy of this CRF will be provided as a worksheet. All data will be recorded into electronic CRFs. The study coordinator or data coordinator will use an internet browser to key data directly into Rho's internet-based remote data entry system. Univariate data validation tests are performed as the data are keyed and most implausible data values are resolved immediately. Data are not stored on the site's computer. At the end of each "page," data are submitted to Rho's secure web server and stored in the study's database. The database is backed up nightly; backup tapes are saved in a secure, off-site location. At any time site personnel can log into the system, review and correct previously entered data, key additional data, or lock records to prevent further inadvertent medications. The pages will be accessible via the CSCC website and require Center-specific user ID/password privileges.

CRF data must be currently maintained and up-to-date. Study participants must not be identified by name on any study documents. Patients will be assigned and identified by CSCC patient numbers assigned at the time of initial enrollment into a CSCC study.

### 12.2 DATA MANAGEMENT

The SDMC will provide statistical and data management support for the study. Validation rules will be applied at several points in the data management process. An error correction procedure will be applied to correct data values that fail validation rules.

### 12.3 TRAINING AND DATA MONITORING

Prior to the onset of screening, clinical staff (coordinators and psychologists) will be centrally trained to ensure adherence to the protocol and assure highest possible data quality. Training will be led by a combination of investigators and other staff from the clinical centers and the SDMC. Training presentations will address informed consent procedures, study operations and protocol requirements, data collection procedures, maintenance of source documentation, CRF completion and review, routine reporting requirements, electronic data capture, and CSCC and NHLBI policies and procedures. Re-training of existing staff or training of new project staff will occur at annual intervals in conjunction with annual meetings. When central training sessions cannot be arranged, study-specific training will occur over the telephone, either during teleconferences or during individual conversations. As needed and as time allows, face-to-face training will be provided by SDMC staff as part of periodic site visits.

After central training, individual sites will monitor CRFs and source documents for accuracy, protocol compliance, subject safety, and adherence to guidelines outlined in the CSCC Manual of Procedures.

As referenced above, centers will be site-visited. Presently, plans for clinical data monitoring include, at a minimum, one site visit for each site during the cross-sectional and again for the pilot transfusion study phase once the study is underway. At each site visit, recruitment guidelines and study eligibility criteria will be reviewed. Additionally, completed data forms will be reviewed and compared to source documentation (medical or center records) to confirm accuracy. A detailed description of the activities and procedures for monitoring this study are described in the Neuropsychological Dysfunction and Neuroimaging Abnormalities in Neurologically Intact Adult Patients With Sickle Cell Disease (SCD) Clinical Monitoring Plan.

Apart from the training for clinical coordinators and psychologists, a procedure for site qualification for MRI completion will be implemented by scientists at the central reading center. The steps in qualification will consist of completion of a questionnaire about the local scanner, scanning a phantom and sending the reading to the central facility, and scanning and re-scanning a volunteer for test/retest reliability assessment.

The DSMB will receive reports concerning recruitment and other issues every six months. A month prior to the scheduled meeting time, the SDMC will synthesize all available data and generate a report of all relevant information. This report will be available to the DSMB at least two weeks prior to the scheduled meeting time. In addition to recruitment and participation data, this report will include all AEs (Section 12). Upon review of the study data, the DSMB will make recommendations to the PI. In addition to routine reports, the transfusion study will be stopped pending consultation with the DSMB in the event of the occurrences outlined in Section 12.

## 13 STATISTICAL ANALYSIS

### 13.1 SAMPLE SIZE

The primary comparison is a difference in mean scores on the WAIS-III PIQ between adult SCD patients and community-based controls, after adjustment for age and years of education. Our preliminary data in children showed that even patients with normal MRI studies had a mean WAIS-III PIQ score of 87 (with a standard deviation of 20), close to one standard deviation below the normative mean of 100. The patients with silent infarctions on MRIs had a mean score of 75 (with a standard deviation of 11). We therefore would predict that our population of adults, some of whom will have abnormal MRI studies, will have a mean score of 85 or less and a standard deviation of 15. Although there are limited data, we would expect that the community control group of similar age and education level will have a mean of 100 with a standard deviation of 15. The discussion and tables below illustrate sample sizes (and associated power calculations) needed in order to detect varying magnitudes of differences in the mean score of our patients from the control group, with two different assumptions about the standard deviations. The calculations presented are based on the assumption that the ratio of patients to controls will be roughly 3:1.

For power calculations and statistical analysis, the primary hypothesis, adult SCD patients will have a mean WAIS III PIQ different from the mean of the community based control group adjusted for site, sex, age and years of education can be expressed:

$$H_0: \mu_{\text{control}} - \mu_{\text{SCD}} = 0$$

$$H_a: \mu_{\text{control}} - \mu_{\text{SCD}} \neq 0.$$

Although we will use a GLM to test the primary hypothesis, we used a 2-sample comparison t-test framework for power calculations. If the matching ensures homogeneity between the SCD patients and the control group except for SCD status, then for any choice of power the necessary sample size for the GLM will be smaller than what is predicted in this sample size analysis. To estimate the sample size needed per group to detect a 15 percentage point difference in two unequally sized groups using a 2-sided t-test (see Table 13.1), we used the following approximate sample size calculation algorithm:

$$1) \text{ Calculate } m: m = \frac{2(z_{1-\alpha/2} + z_{1-\beta})^2 \sigma^2}{|\mu_1 - \mu_2|^2}.$$

2) Let  $n_1$  = sample size for group 1, and  $n_2$  = sample size for group 2.

3) Calculate  $n_1 = m(k+1)/2k$  and  $n_2 = kn_1$ .

**TABLE 13.1 Sample Size Calculations for a 2-Sided t-test with an SD of 15 and  $n_2 = 0.3n_1$**

Difference in mean WAIS-III Performance IQ between adults with SCD and the control group.	Sample sizes required in each group (2-sided) Cases, Controls*	Power
8	120, 36	0.80
8	137, 42	0.85
8	161, 49	0.90
8	198, 60	0.95
10	77, 24	0.80
10	88, 27	0.85
10	103, 31	0.90
10	127, 39	0.95
15	35, 11	0.80
15	39, 12	0.85
15	46, 14	0.90
15	57, 18	0.95

\* *Sample Size Estimates Assuming 3 Controls for Every 10 Cases (these do not take data loss into account).*

 Lloyd D. Fisher, Gerald van Belle, *Biostatistics A Methodology For The Health Sciences*, Wiley Science Paperback Series, (New York: John Wiley & Sons, Inc., 1993), 190-191.

**TABLE 13.2 Sample Size Calculations for a 2-Sided t-test with an SD of 20 and  $n_2 = 0.3n_1$**

Difference in mean WAIS-III Performance IQ between adults with SCD and the control group.	Sample sizes required in each group (2-sided) Cases, Controls*	Power
8	213, 64	0.80
8	244, 74	0.85
8	285, 86	0.90
8	352, 106	0.95
10	137, 42	0.80
10	156, 47	0.85
10	183, 55	0.90
10	226, 68	0.95
15	61, 19	0.80
15	70, 21	0.85
15	81, 25	0.90
15	101, 31	0.95

\* *Sample Size Estimates Assuming 3 Controls for Every 10 Cases. (These do not take data loss into account).*

Observations:

1. If the standard deviation of the WAIS-III is no greater than 15 and the true difference in WAIS III group means is at least eight, then using 120 SCD patients and 36 controls results in at least 80% power for the primary hypothesis.
2. If the standard deviation of the WAIS-III is no greater than 20 and the true difference in WAIS III group means is at least 15, then using 101 SCD patients and 31 controls results in at least 95% power for the primary hypothesis (see Table 13.2).

In order to have sufficient power for the primary hypothesis and sufficient patients recruited for the 4th secondary hypothesis (transfusion study) we would need to enroll 150 patients and 45 controls. Assuming an 80% completion rate, 120 patients and 36 controls would complete the baseline evaluation. (Please refer to observations 1 and 2 above for power estimates.) Assuming a normal distribution, 60 of the 120 patients will have WAIS-III PIQ scores at or below the predicted mean of 85. These patients would be approached to participate in the transfusion study. Assuming 60% would agree to participate and again assuming a completion rate of 80%, 36 patients would be randomized to either the chronic transfusion arm or the standard care arm and 30 would complete the protocol (allowing for 15 in each group).

For power calculations and statistical analysis the 4th secondary hypothesis, the transfusion arm will have a mean WAIS-III PIQ change score that is different than the mean change score in the control arm, can be expressed:

$$H_0: \mu_{\text{diff, trt}} - \mu_{\text{diff, control}} = 0$$

$$H_a: \mu_{\text{diff, trt}} - \mu_{\text{diff, control}} \neq 0.$$

We will use a 2-sample comparison t-test framework for power calculations. To estimate the power of the t-test given 15 subjects per arm, we used the following normal approximation:

1. Choose a mean change score difference under the alternative,  $H_{a, \text{diff}}$ .

2. Calculate the expected variance of the within subject change score:

$$V(d_i) = V(\text{WAIS}_{i, \text{After}}) + V(\text{WAIS}_{i, \text{Before}}) - 2 \cdot \rho_{\text{WAISAfter, Before}} \sqrt{V(\text{WAIS}_{i, \text{After}})} \cdot \sqrt{V(\text{WAIS}_{i, \text{Before}})}$$

where  $V(\text{WAIS}_{i, x})$  is the WAIS variance for the  $i^{\text{th}}$  subject at time  $x$ .

3. Calculate the expected variance of difference in mean change scores:

$$V(\bar{d}_{\text{trt}} - \bar{d}_{\text{control}}) = V(d_i) \left( \frac{1}{15} + \frac{1}{15} \right)$$

4. Using an alpha of 0.05 calculate the critical value needed to reject the hypothesis under the null:  $0 + 1.96 \cdot \sqrt{V(\bar{d}_{\text{trt}} - \bar{d}_{\text{control}})} = a_{\text{crit}}$

5. Calculate power:

$$\Pr \left[ \left| \bar{d}_{\text{trt}} - \bar{d}_{\text{control}} \right| > a_{\text{crit}} \mid E(\bar{d}_{\text{trt}} - \bar{d}_{\text{control}}) = H_{a, \text{diff}} \right] = 1 - \Phi \left[ \frac{-a_{\text{crit}} - H_{a, \text{diff}}}{\sqrt{V(\bar{d}_{\text{trt}} - \bar{d}_{\text{control}})}} \leq Z \leq \frac{a_{\text{crit}} - H_{a, \text{diff}}}{\sqrt{V(\bar{d}_{\text{trt}} - \bar{d}_{\text{control}})}} \right]$$

where  $\Phi$  is the cumulative distribution function for the normal distribution.

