**Phase I Completion:** On February 22, 2008 enrollment into Phase I was completed with 120 cases and 32 controls. Enrollment and randomization into Phase II is dependent on the values obtained during Phase I, including the initial chemistry/hematology panel, MMSE, POMS, PIQ, and normal MRI. Subjects who enroll in Phase II more than 6 months (but less than 1 year) from completion of Phase I (as determined by date of WAIS-III PIQ) repeat selected assessments upon entry into Phase II. Subjects who were never enrolled in Phase I (or who completed Phase I more than 1 year ago) may also be enrolled in Phase II, per a revised set of inclusion/exclusion criteria that combine Phases I and II. The most non-invasive and least time-consuming screening assessments are completed first to ensure eligibility, before the subject moves forward with additional study procedures.

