**TABLE 5.3 Patients With Evidence of a Silent Infarct (N=13)**

Cognitive	Min.	Max.	Mean	Std. Deviation
WISC-R Verbal IQ	79	113	96.00	17.00
WISC-R Performance IQ	79	113	96.00	17.00
WISC-III Verbal IQ	70	109	91.67	19.86
WISC-III Performance IQ	58	100	78.60	18.89
Woodcock Johnson —R Achievement				
Letter-Word	64	94	74.83	10.65
Reading Comprehension	60	115	85.13	19.25
Arithmetic Problems	54	123	85.14	23.30
Calculations	66	107	84.40	19.09
Fine Motor	49	119	82.29	26.85
Purdue (R)	7	14	10.60	2.88
Purdue (L)	7	14	10.60	2.88
Tactile	8	12	9.25	1.89
Benton (R)	3	10	6.71	2.36
Benton (L)	2	10	6.43	2.99

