## 7 STUDY DESIGN

### 7.1 DESCRIPTION OF PRIMARY AND SECONDARY ENDPOINTS

The primary endpoint is completion of baseline WAIS III-PIQ studies in 120 subjects and 36 controls. Assuming a 20% attrition rate, 150 subjects and 45 controls will be recruited.

Secondary endpoints include completion of the entire baseline NP battery and MRI studies in 120 subjects and 36 controls. After consent and randomization, the final secondary endpoint is completion of the transfusion protocol and demonstration of at least an average five-point within-subject improvement in WAIS-PIQ above any average within-subject improvement observed in the standard care group, total number of patients is 30 (15 in each group). Thirty-six patients meeting these criteria will be randomized, assuming 80% completion. Randomization in the transfusion phase of the study is appropriate in order to discriminate, as much as possible, intervention effects from re-test effects.

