## 13.2 STATISTICAL METHODS

The primary clinical hypothesis is that the mean score for adult patients with SCD on the WAIS-III PIQ scale will be at least one standard deviation below the mean score of a group of community controls matched for site, age, and education. We expect the adult patients with SCD will have a mean WAIS-III PIQ of 85 or less and the community control group will have a mean of 100. Although the primary hypothesis expresses the expected direction of effect, the statistical analysis will follow common practice and use a 2-sided hypothesis test with an alpha of 0.05.

To test the primary hypothesis, we will use a GLM to model the data. At each site participating in this study we will match the patients using a ratio of 3 patients to 1 community controls, but if necessary we will still statistically control for site, age, sex, and education. Model selection techniques will be used to determine the most parsimonious models. For statistical analysis we express the primary hypothesis, adult SCD patients will have an adjusted mean WAIS-III PIQ different from the community based control group adjusted mean WAIS-III PIQ (based on the final model):

$$H_0: \text{Adj\_}\mu_{\text{SCD}} - \text{Adj\_}\mu_{\text{control}} = 0$$

$$H_a: \text{Adj\_}\mu_{\text{SCD}} - \text{Adj\_}\mu_{\text{control}} \neq 0.$$

The first secondary hypothesis is the same as the primary hypothesis with other NP tests being used as the response; therefore, the analysis for these hypotheses will be the same as the primary hypothesis.

The 2nd secondary hypothesis is that patients with SCD and abnormal MRIs will have a higher proportion of abnormal NP test results than the patients with SCD and normal MRIs. The statistical analysis of this hypothesis will follow common practice and use a 2-sided hypothesis test with an alpha of 0.05. For statistical analysis we express this secondary hypothesis as:

Cortical gray matter volume, hippocampal volume, white matter lesions (WML), cortical strokes, and lacunar infarcts will correlate with cognitive function (memory and executive function).

$$H_0: \rho_{\text{MRI-NPtest}} = 0$$

$$H_a: \rho_{\text{MRI-NPtest}} \neq 0.$$

For this analysis, we will use Spearman correlations, Pearson correlations, and/or multiple regression.

The 3rd secondary hypothesis involves comparing the ability of regular MRI and VMRI to predict neurocognitive injury. The 3rd secondary hypothesis is:

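### Phase I closed with 32 controls, but the primary endpoint and Observation 1 still assume 36; Section 13.1 also misquotes a pilot Performance IQ figure

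*Protocol*

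**What the plan says.** - **Endpoint.** Section 7.1: "The primary endpoint is completion of baseline WAIS III-PIQ studies in 120 subjects and 36 controls". The Synopsis (Criteria for Evaluation) says the same. Both plan to recruit 150 and 45 to allow for 20% attrition.
- **Power.** Section 13.1, Observation 1, sets two conditions, an SD of 15 or less and a true gap of 8 points or more, and concludes: "then using 120 SCD patients and 36 controls results in at least 80% power for the primary hypothesis". Observation 2 claims at least 95% power for 15 points at SD 20 with 101 cases and 31 controls.
- **Actual enrolment.** Synopsis, Phase I Completion: "On February 22, 2008 enrollment into Phase I was completed with 120 cases and 32 controls". Section 8.8 adds that people who had consented and completed Visit 1 could still finish Visits 2 to 4. The 120 and 32 are therefore people enrolled, not people tested.
- **Pilot basis.** Section 13.1 takes a mean of 87 (SD 20) for children with normal MRI, and then: "The patients with silent infarctions on MRIs had a mean score of 75 (with a standard deviation of 11". It calls these scores WAIS-III. From them it predicts a mean of 85 or less and an SD of 15 in adults with SCD. The source, Table 5.3 ("Patients With Evidence of a Silent Infarct (N=13"), shows WISC-III Performance IQ 78.60 (SD 18.89).
- **Phase II.** Section 13.1, at 80% completion: "36 patients would be randomized to either the chronic transfusion arm or the standard care arm and 30 would complete the protocol".

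**The concern.** The current text disagrees with itself. One part of the Synopsis reports 32 controls enrolled. Another part, with Sections 7.1 and 13.1, still works from 36 controls completing. If the endpoint is read literally as a completion count, it is out of reach whatever the PIQ data show. It also differs from what Section 13.2 tests, which is an adjusted difference in mean PIQ. A reader facing a small or borderline Phase I difference would take the 80% from Observation 1, although the enrolled sample does not provide it.

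The pilot misquote matters because the prediction of SD 15 follows directly from it. SDs of 20 and 11 make 15 look like a midpoint. The tabulated WISC-III values for the same two groups, 20.20 and 18.89, both lie above 15.

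**Working it through.** **Inputs.** Two-sided test at 5% (Section 13.2: "use a 2-sided hypothesis test with an alpha of 0.05"); differences of 8 and 15 points and SDs of 15 and 20 (Section 13.1); 120/36 planned, 120/32 enrolled.

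**Formula.** Section 13.1 uses a two-sample framework with a normal approximation: SE = SD × √(1/n₁ + 1/n₂), power ≈ Φ(difference/SE − 1.96).

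**Reproducing the plan.** At 120/36 and SD 15, SE = 15 × √(1/120 + 1/36) = 2.850. 8/2.850 = 2.807, and Φ(2.807 − 1.96) = 80.1%. Observation 1 is correct on its own terms (79.7% with a noncentral t). Every row of Tables 13.1 and 13.2 also reproduces. For Observation 2, 101/31 at SD 20 and 15 points gives 95.5%.

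**At the enrolled numbers.** At 120/32 and SD 15, SE = 15 × √(1/120 + 1/32) = 2.984. 8/2.984 = 2.681, and Φ(0.721) = 76.4% (75.9% with t).

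| Scenario | 120/36 | 120/32 |
|---|---|---|
| 8 points, SD 15 | 80.1% | 76.4% |
| 8 points, SD 20 | 55.8% | 52.0% |
| 15 points, SD 20 | – | 96.5% |
| 15 points, SD 15 | – | 99.9% |
| Difference detectable with 80% power, SD 15 | 7.99 | 8.36 |
| Difference detectable with 80% power, SD 20 | 10.65 | 11.15 |

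The last two rows are (1.960 + 0.842) × SE.

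**Two influences the protocol does not quantify.**
- Non-completion: if 80% of those enrolled completed (an assumption, about 96/26), SE = 3.316 and power for 8 points at SD 15 is 67%. With no loss it is 76.4%.
- Covariate adjustment: if the covariates explained 10% of the variance (an assumption), the residual SD is 15 × √0.9 = 14.23, SE = 2.831 and power is about 81%. If they explain nothing, it stays at 76.4%.

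**Pilot figures.**

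| Group | Section 13.1 | Table, WISC-III Performance IQ |
|---|---|---|
| No stroke | 87 (SD 20) | 86.56 (SD 20.20), Table 5.2 |
| Silent infarct | 75 (SD 11) | 78.60 (SD 18.89), Table 5.3 |

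The first row is a fair rounding; the second is not. The Letter-Word achievement row of Table 5.3 reads 74.83 (SD 10.65), which rounds to 75 and 11. A copied row is the likely cause, but that is an inference.

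**Phase II.** 36 × 0.80 = 28.8, and 30 completers would need 30/0.80 = 37.5, so 38. Phase I divides correctly: 120/0.80 = 150. By the protocol's method, the change-score variance is 2 × 15² × (1 − ρ):
- ρ = 0.80, 10 points: variance 90. With 15 per arm SE = √(90 × 2/15) = 3.464 and power is 82.3% (82% stated). With 14 per arm SE = 3.586 and power is 79.6%.
- ρ = 0.70, 5 points: variance 135. With 15 per arm power is 21.8% (22% stated). With 14 per arm it is 20.7%.

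**The case against.** The strongest defence is that Observation 1 is a conditional planning statement and its arithmetic is right. The 32 controls are disclosed openly, and 8 points is the smallest scenario tabulated, well below the 15 points that the protocol expects. Section 13.1 also says the adjusted model should need fewer subjects if matching works. All of this stands. It limits the size of the problem, but the text still gives a sample and a power that the enrolled numbers do not match.

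Four stronger readings are tempting, and the document does not support them.

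- *The stated powers fail throughout.* They do not. Observation 2 is exceeded at 120/32, the expected 15-point difference has at least 96% power, and the Phase II powers are computed correctly for 15 per arm.
- *SD 15 rests on the misquote.* This is not shown. Section 13.1 also quotes the SD of 20, assumes 15 for controls too, describes 87 as nearly one SD below 100, and gives a full table at SD 20. Nor does the pilot as a whole point to 20: other Performance IQ SDs are 13.29 (WISC-R, Table 5.2), 17.00 (WISC-R, Table 5.3) and 11.78 (WISC-III, stroke group, Table 5.4). All are paediatric.
- *The study has already failed its primary endpoint.* This holds only for the literal completion count. The quantity tested is the adjusted PIQ difference, and Section 8.1 calls the numbers approximate.
- *Phase II power for 10 points falls from 82% to 77%.* That combines fewer completers with a change to a t-test. The t-test alone, at 15 per arm, gives 79.6%.

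On the Phase II count, Section 13.1 obtains 36 as 60% of 60 patients, and the shortfall is 1.2 patients against numbers called approximate elsewhere. It is a slip, not a design fault.

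**Conclusion.** The point holds in a limited form. With 32 controls enrolled, the 120/36 completion endpoint cannot be met. For 8 points at SD 15, unadjusted power is at most about 76% rather than at least 80%, a loss of roughly 4 percentage points. The 76% assumes that everyone enrolled was tested and that covariates explain no variance; the first assumption is favourable and the second unfavourable. At SD 20 the same difference has about 52%. Conclusions about a 15-point difference are unaffected.

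The silent-infarct figure in Section 13.1 is wrong against its own source table, and so is the WAIS-III label for these children's scores. The two WISC-III values that the section draws on do not bracket 15, although SD 20 is already tabulated. The Phase II completer count is a minor error that lowers the stated powers by about 1 to 3 percentage points.

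**What to change.** 1. In the Synopsis and Section 7.1, define the primary endpoint as the WAIS-III PIQ score, compared as the adjusted case-control difference in means. Describe 120/36 as a target for which enrolment closed at 120/32.
2. Restate Observation 1 at 120/32: about 76% (SD 15) and 52% (SD 20) for 8 points, and at least 96% for 15 points at either SD. Add that covariate adjustment may raise these figures and non-completion would lower them.
3. In Section 13.1, correct the silent-infarct figure to 78.60 (SD 18.89) and label the pilot scores WISC-III. Justify SD 15 on grounds other than these two groups, or give SD 20 equal standing.
4. State about 28 to 29 Phase II completers. At 14 per arm, by the protocol's normal method, power is about 80% (10 points, ρ 0.80) and 21% (5 points, ρ 0.70).

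The cost is protocol wording and a less favourable stated power. No enrolment, procedure or analysis changes.
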